5.4.2 Phase I studies in adults

ST10-01-101 study

Another open-label, randomized Phase 1 study evaluated the pharmacokinetics of Ferric Maltol and its effect on iron indices in patients with iron deficiency (with or without anemia). 24 subjects received Ferric Maltol 30, 60, or 90 mg BID over an 8-day period. PK and iron uptake were assessed on Days 1 and 8. Ferric maltol showed predictable pharmacokinetics, no accumulation over 7 days, and improvements in iron uptake across the dose range 30–90 mg BID (Bokemeyer, 2016).

The PK data from this study are consistent with previous data indicating that maltol is rapidly glucuronidated and renally excreted after ST10 dosing, while iron is independently absorbed. Across the three dosing regimens investigated, exposure to maltol glucuronide increased dose proportionally. Serum iron concentrations and TSAT values generally increased with higher doses, but there was no clear relationship between these parameters and exposure to maltol or maltol glucuronide. Higher NTBI levels were detected in the higher dosing regimens. Although the frequency of AEs was also higher with these dosing regimens, there is no evidence that this was a consequence of elevated NTBI in these subjects. The reported AEs were consistent with the established safety profile of ST10.

ST10-01-102 study

The study results showed that plasma and urinary PK parameters for maltol and maltol glucuronide were consistent with rapid metabolism of maltol to maltol glucuronide, followed by renal excretion. Total serum iron and TSAT increased after ST10 dosing, although there was no clear relationship between either of these parameters and exposure profile to maltol or maltol glucuronide. There was no evidence of intact ST10 in serum samples, as measured indirectly by NTBI, and there were no findings in this sub-study that affected the safety profile of ST10.

The low serum NTBI values are consistent with the safety profile of ST10. Unsurprisingly, given the short duration, there were no significant safety findings in this sub-study.

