7 INVESTIGATIONAL PLAN

7.1 STUDY OVERVIEW

This is a, Phase I, randomized, open-label, single dose, four-way crossover study, to compare the pharmacokinetics of iron and maltol absorption from ferric maltol capsules and oral suspension under fasted and fed conditions in adult healthy volunteers

The study will comprise of the following stages:

- Screening: up to 14 days
- Randomized treatment:

A treatment period of 4 days with at least 48 hrs washout period between dose administration.

During the crossover PK phase, subjects will be randomized in a 1:1:1:1 ratio to receive one of the following treatment sequences. 8 subjects will be randomized to each sequence:

Sequence A:

- *Period 1; single dose of 30 mg ferric maltol capsule in a fed condition*
- *Period 2; single dose of 30 mg (5 ml) ferric maltol suspension in a fed condition*
- *Period 3; single dose of 30 mg ferric maltol capsule in a fasted condition*
- *Period 4; single dose of 30 mg (5 ml) ferric maltol suspension in a fasted condition*

Sequence B:

- *Period 1; single dose of 30 mg (5 ml) ferric maltol suspension in a fasted condition*
- *Period 2; single dose of 30 mg ferric maltol capsule in a fed condition*
- *Period 3; single dose of 30 mg (5 ml) ferric maltol suspension in a fed condition*
- *Period 4; single dose of 30 mg ferric maltol capsule in a fasted condition*

Sequence C:

- *Period 1; single dose of 30 mg ferric maltol capsule in a fasted condition*
- *Period 2; single dose of 30 mg (5 ml) ferric maltol suspension in a fasted condition*
- *Period 3; single dose of 30 mg ferric maltol capsule in a fed condition*
- *Period 4; single dose of 30 mg (5 ml) ferric maltol suspension in a fed condition*

Sequence D:

- *Period 1; single dose of 30 mg (5 ml) ferric maltol suspension in a fed condition*
- *Period 2; single dose of 30 mg ferric maltol capsule in a fasted condition*

- *Period 3; single dose of 30 mg (5 ml) ferric maltol suspension in a fasted condition*
- *Period 4; single dose of 30 mg ferric maltol capsule in a fed condition*

Prior to the first treatment period, subjects will arrive at the Clinical Unit on Day -1 at least 13 hrs before dosing. After at least 10 hours overnight fasting at the Clinical Unit subjects will be randomized to one of the 4 treatment sequences. PK samples will be collected pre-dose and up to 24 hrs post-dose during each period (11 times) for the measurements of serum iron, TSAT, TIBC, UIBC, transferrin, plasma maltol and maltol glucuronide.

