8.3.2 WASHOUT PERIOD

Washout period lasts for at least 48 hrs between dose administration.

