6. Breath test will be performed at Screening and at Period 1 Day -1 to measure the Breath Alcohol Content (BAC) of each subject.
7. Eligibility central laboratory sampling/assessments must be completed at Screening and on Period 1 Day -1 before the subject is randomized.
8. Hematology, Clinical Chemistry and screening Iron markers blood sampling
9. On all four PK study days, all subjects will have baseline PK blood samples collected immediately prior to Ferric Maltol dosing (0 hr). Subjects will then have further PK blood samples collected at 11 additional times after dosing; the post-dose PK sample times will be 15 mins \pm 2 min, 30 mins \pm 2 min, 45 mins \pm 5 min, 1 hr \pm 5 min, 1.5 hr \pm 5 min, 2 hrs \pm 5 min, 3 hrs \pm 5 min, 4 hrs \pm 5 min, 6 hr \pm 10 min, 10 hrs \pm 15 min and 24 hrs \pm 15 min. For each individual subject, the post-dose PK blood sampling schedule will be the same on all four PK days. PK blood samples on the PK days will be: serum iron, total and unsaturated iron binding capacity (TIBC, UIBC), transferrin, transferrin saturation (TSAT), maltol and maltol glucuronide.
10. Drug dispensing: subjects will be randomized to either Sequence A, B, C or D

Sequence A:

- Period 1; single dose of 30 mg ferric maltol capsule in a fed condition
- Period 2; single dose of 30 mg (5 ml) ferric maltol suspension in a fed condition
- Period 3; single dose of 30 mg ferric maltol capsule in a fasted condition
- Period 4; single dose of 30 mg (5 ml) ferric maltol suspension in a fasted condition

Sequence B:

- Period 1; single dose of 30 mg (5 ml) ferric maltol suspension in a fasted condition
- Period 2; single dose of 30 mg ferric maltol capsule in a fed condition
- Period 3; single dose of 30 mg (5 ml) ferric maltol suspension in a fed condition
- Period 4; single dose of 30 mg ferric maltol capsule in a fasted condition

Sequence C:

- Period 1; single dose of 30 mg ferric maltol capsule in a fasted condition
- Period 2; single dose of 30 mg (5 ml) ferric maltol suspension in a fasted condition
- Period 3; single dose of 30 mg ferric maltol capsule in a fed condition
- Period 4; single dose of 30 mg (5 ml) ferric maltol suspension in a fed condition

Sequence D:

- Period 1; single dose of 30 mg (5 ml) ferric maltol suspension in a fed condition
- Period 2; single dose of 30 mg ferric maltol capsule in a fasted condition
- Period 3; single dose of 30 mg (5 ml) ferric maltol suspension in a fasted condition

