12 STATISTICAL CONSIDERATIONS

12.1 SAMPLE SIZE AND POWER CALCULATIONS

The sample size is based on the comparisons of each of the primary PK parameters C_{max} and AUC_{last} for total serum iron between the formulations, within each of the two conditions: fed and fasted. Each comparison will be made via the ratio of the two values of the parameter between the formulations. The 90% confidence interval (CI) for this ratio will be reported.

For each of the two comparisons (suspension vs capsule (fed condition); suspension vs capsule (fasted condition)) the CIs for two parameter ratios (C_{max} and AUC_{last}) for serum iron will be calculated, making a total of 4 CIs. If these ratios were all independent, and the probability of being within (80%, 125%) was 80% for each, then the probability that all 4 would fall within the required limits would be $(80\%)^4 = 41\%$. With individual probabilities of 90%, the combined probability would be 66%. However, if the ratios were positively correlated, the combined probabilities would be higher.

Data from a previous study (ST10-01-101) were used to provide estimates of the standard deviations (SDs) of the logs of the within-subject ratios of the parameters C_{max} and AUC_{last} , for both total serum iron and TSAT. Assuming the SD is no greater than 0.38, if the true ratio is 1, 31 subjects would provide a probability of at least 80% of all 4 CIs lying within (80%, 125%).

The aim of the study is to demonstrate that the 4 CIs for serum iron are all within (80%, 125%). As the SD, and the degree of correlation, are uncertain, 32 subjects will be recruited to the study.

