2.2 Study Design

2.2.1 *Study Overview*

This is a Phase I, randomized, open-label, single dose, four-way crossover study, to compare the pharmacokinetics of iron and maltol absorption from ferric maltol capsules and oral suspension formulations under fasted and fed conditions in adult healthy volunteers.

A total of 32 eligible subjects will be randomized at a ratio of 1:1:1:1 to receive one of the following treatment sequences comprised of four treatment periods. Treatment periods will last 4 days with at least 48 hours washout period between each dose administration. Eight subjects will be randomized to each treatment sequence:

Sequence A:

- Period 1; single dose of 30 mg ferric maltol capsule in a fed condition
- Period 2; single dose of 30 mg (5 ml) ferric maltol suspension in a fed condition
- Period 3; single dose of 30 mg ferric maltol capsule in a fasted condition
- Period 4; single dose of 30 mg (5 ml) ferric maltol suspension in a fasted condition

Sequence B:

- Period 1; single dose of 30 mg (5 ml) ferric maltol suspension in a fasted condition
- Period 2; single dose of 30 mg ferric maltol capsule in a fed condition
- Period 3; single dose of 30 mg (5 ml) ferric maltol suspension in a fed condition
- Period 4; single dose of 30 mg ferric maltol capsule in a fasted condition

Sequence C:

- Period 1; single dose of 30 mg ferric maltol capsule in a fasted condition
- Period 2; single dose of 30 mg (5 ml) ferric maltol suspension in a fasted condition
- Period 3; single dose of 30 mg ferric maltol capsule in a fed condition
- Period 4; single dose of 30 mg (5 ml) ferric maltol suspension in a fed condition

Sequence D:

- Period 1; single dose of 30 mg (5 ml) ferric maltol suspension in a fed condition
- Period 2; single dose of 30 mg ferric maltol capsule in a fasted condition
- Period 3; single dose of 30 mg (5 ml) ferric maltol suspension in a fasted condition
- Period 4; single dose of 30 mg ferric maltol capsule in a fed condition

The planned study consists of three study phases:

1. Screening Phase;
2. Treatment Phase;
3. Follow-Up Phase.

Table 1 contains details of the study periods, study visits and timing of the visits.

Table 1 Study Visits

Phase	Period	Study Visit	Study Day
Screening	Screening	1	-14 to -1
Treatment	Treatment Period 1	2	1
	Treatment Period 2	3	3
	Treatment Period 3	4	5
	Treatment Period 4	5	7
Follow-Up	Follow-Up	6	10-14

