3.2 Baseline

Baseline is defined as reading or measurements at Day 1 prior to study drug administration of each period. If the reading at Day 1 predose is missing, the last reading before first dosing will be set as baseline.

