3.5.5 PK analysis

To compare the pharmacokinetics of ferric maltol capsules and oral suspension under fasted and fed conditions, a subject must have a calculable PK parameter for both formulations under fasted or fed condition.

An ANOVA model will be performed on the ln-transformed PK parameters (C_{\max} , AUC_{last} and AUC_{inf}) of the two formulations including terms for sequence (treatment sequence), treatment (formulation/condition), and period as fixed effects, and subjects nested within a sequence as a

random effect. The estimates will be back-transformed into original scale. The point estimates for ratios and the corresponding 90% CIs will be provided.

The PK parameters analyses will be based on the FAS Population.

The sample SAS code for this analysis is included here for $\alpha = 0.10$:

```
proc mixed;
  class subject treatment sequence period;
  model logPKvar = treatment sequence period /ddfm=Satterthwaite; random
  subject(sequence);
  lsmeans treatment/pdiff cl alpha=0.1;
  run;
```

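### The four sequences are rotations of one order, so unequal carry-over enters both primary suspension/capsule ratios with weight 0.75; a Williams square of the same size cuts this to 0.25 and cancels carry-over due to food state

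*Protocol*

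**What the plan says.** Protocol 7.1 fixes the allocation: "subjects will be randomized in a 1:1:1:1 ratio to receive one of the following treatment sequences. 8 subjects will be randomized to each sequence". The same four sequences appear in the Synopsis, in Protocol 5.5.2, 8 and 10.2, and in SAP 2.2.1 (for Sequence A, for example: "Period 2; single dose of 30 mg (5 ml) ferric maltol suspension in a fed condition").

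The primary comparisons are suspension against capsule for Cmax and AUClast of total, uncorrected serum iron, once fed and once fasted. Protocol 12.1 sets the aim that all four 90% CIs fall within 80-125%.

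SAP 3.5.5 analyses the log parameters with a model "including terms for sequence (treatment sequence), treatment (formulation/condition), and period as fixed effects", and with subject within sequence as a random effect. There is no term for the preceding treatment. Protocol 8.3.2 gives the protection between doses: "Washout period lasts for at least 48 hrs between dose administration". Neither document mentions carry-over or explains the choice of sequences.

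**The concern.** In a four-period crossover, the choice of sequences decides which treatment comes before which. If each treatment always follows the same one, its own effect is mixed with the residual effect of that predecessor. Here suspension and capsule follow different predecessors within each feeding condition, and those predecessors differ in food state. Protocol 5.3 says the drug is better absorbed on an empty stomach, so if any carry-over exists it could well depend on food state.

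Such carry-over would push the fed ratio one way and the fasted ratio the other, which could pass for a formulation-by-food interaction. It could also move a CI outside 80-125%, or bring one inside, in a trial meant to support interchangeability (Protocol 5.5).

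**Working it through.** **Coding.** 1 = capsule fed, 2 = suspension fed, 3 = capsule fasted, 4 = suspension fasted. From Protocol 7.1: A = 1-2-3-4, B = 4-1-2-3, C = 3-4-1-2, D = 2-3-4-1.

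**Predecessors.** After Period 1 only four of the 12 possible ordered pairs occur: 1→2, 2→3, 3→4 and 4→1, three times each.

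**Bias under the SAP model.** Each treatment occurs once per sequence and once per period. With complete data, a treatment contrast is therefore the difference of two means, each over four sequence-period cells. Write λ for the log carry-over of the preceding treatment.

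- Fed: suspension follows 1 in three of its four cells and is first in the other; capsule follows 4 in three of four. Bias = ¾λ1 − ¾λ4 = 0.75(λ1 − λ4).
- Fasted: suspension follows 3 and capsule follows 2, each in three of four cells. Bias = 0.75(λ3 − λ2).
- If carry-over depends only on food state, the biases are 0.75(λfed − λfasted) and 0.75(λfasted − λfed): equal size, opposite sign. If all λ are equal, both are zero.

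**The same for a Williams square** (1-2-4-3, 2-3-1-4, 3-4-2-1, 4-1-3-2; all 12 ordered pairs once).

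- Fed: ¼(λ1 + λ3 + λ4) − ¼(λ2 + λ3 + λ4) = 0.25(λ1 − λ2).
- Fasted: 0.25(λ3 − λ4).
- Carry-over that depends only on food state cancels in both.

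Least squares on the full 128-row design (32 subjects × 4 periods) gives the same weights.

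**Cost of adjusting.** Contrast variance from the same design, in units of residual variance divided by 8:

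| Model | Current | Williams |
|---|---|---|
| SAP 3.5.5 | 0.50 | 0.50 |
| + food state of preceding dose | 1.625 (×3.25) | 0.50 |
| + full four-level carry-over | 2.75 (×5.5) | 0.55 (×1.1) |

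Period 1 keeps the contrasts estimable on the current layout. With the planning SD of 0.38 for the log within-subject ratio (Protocol 12.1), SE = 0.38/√32 = 0.0672. With full carry-over fitted it is 0.0672 × √5.5 = 0.1575, and the 90% half-width is about 0.262, wider than ln 1.25 = 0.223.

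**Pass probability for one CI.** This is the exact probability that the 90% CI lies within 80-125% at a true ratio of 1, with residual df 90 (89 or 87 when carry-over is fitted).

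- No carry-over, SAP model: 90.1% on either layout.
- Food state fitted: 14.9% current, 90.1% Williams.
- Full carry-over fitted: 0.1% current, 86.6% Williams.

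**Effect of carry-over under the SAP model.** The carry-over differences are assumed, because the documents give none. For the current layout d is the difference between the two predecessors. For the Williams square d is the capsule-minus-suspension difference in the same condition.

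| d (log) | Ratio shift, current: exp(0.75d) | Pass, current | Pass, Williams |
|---|---|---|---|
| 0.02 | 1.015 | 89.3% | 90.1% |
| 0.05 | 1.038 | 85.0% | 89.6% |
| 0.10 | 1.078 | 70.4% | 87.9% |
| 0.20 | 1.162 | 28.6% | 81.1% |

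With a paired analysis on 31 df the base is 89.1% and the current-layout values are 88.3, 83.9, 69.2 and 28.1%.

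**The plan's own figures.** The plan states no carry-over figure to reproduce. Its 31 subjects for 80% joint probability is not reproduced by the exact paired calculation (88% per CI and 60% jointly at 31). That is a separate matter and does not affect the weights above.

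**The case against.** The algebra is not in dispute; materiality is. The bias is a fraction of a difference in carry-over, and no document shows that difference to be non-zero. The nearest evidence points the other way. Protocol 5.4.2 says of 30-90 mg twice daily: "Ferric maltol showed predictable pharmacokinetics, no accumulation over 7 days". Here single 30 mg doses are at least 48 hours apart. A log difference of 0.20 would mean that serum iron exposure differs by 22% solely because of the dose two days earlier.

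The SD of 0.38 is also an upper bound. At assumed SDs of 0.30, 0.25, 0.20 and 0.15, the pass probability on the current layout with full carry-over fitted is 12, 38, 70 and 94%. The unadjusted analysis with d = 0.10 keeps 87, 95, 99 and 100%.

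The plan also has a safeguard. A sample is drawn before dosing in every period, and SAP 3.2 says "Baseline is defined as reading or measurements at Day 1 prior to study drug administration of each period". Suspension/capsule ratios of baseline-corrected iron are planned by feeding condition (Protocol Synopsis and 12.2).

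Most of this stands as a limit on size. It does not remove the point. The no-accumulation sentence names no analyte and comes from iron-deficient patients. Baseline correction removes residual iron level but not a change in absorption, and it is secondary while the primary endpoint is uncorrected. The low-SD figures are assumptions too. Nor does the case for change require carry-over to be proven, because the alternative has the same variance.

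**Conclusion.** The concern holds as a design weakness, not as a demonstrated bias. The layout gives weight 0.75 to unequal first-order carry-over in both primary contrasts. At the planning SD, full adjustment leaves a 0.1% chance that a given CI passes. The effect on the trial runs from negligible (d = 0.02) to severe (d = 0.20), and the documents do not show where the truth lies; the evidence they offer favours the low end.

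The figures assume complete data, first-order carry-over that adds on the log scale, a true ratio of 1, 32 subjects and SD 0.38; the adjustment penalty matters less if the SD is well below that. In a Williams square, food-state carry-over cancels only in the suspension/capsule ratios; fed/fasted contrasts keep a weight of 0.25. The change is recommended because it costs almost nothing, not because the trial fails without it.

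**What to change.** **If the list has not been issued:** replace the four sequences with a Williams square on the same treatments, 8 subjects each, with doses and spacing unchanged. An example is 1-2-4-3, 2-3-1-4, 3-4-2-1, 4-1-3-2. Update the Protocol Synopsis, 5.5.2, 7.1, 8 and 10.2, and SAP 2.2.1. Keep the SAP 3.5.5 model as primary and add a full carry-over model as a sensitivity analysis.

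Cost: a new randomisation list and revised text. There are no extra subjects, visits, samples or doses and no loss of precision in the primary model. The sensitivity model has about 10% more variance (0.55 against 0.50).

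**If the list has been issued:** state the limitation in the SAP, and tabulate pre-dose serum iron in Periods 2-4 by preceding treatment, using samples already planned. Report a model with the food state of the preceding dose as supportive only. On the current layout that model has 3.25 times the variance. It also leaves a bias of 0.375 × [(λ1 − λ2) + (λ3 − λ4)] in each contrast, that is, 0.375 times the sum of the fed and fasted capsule-minus-suspension carry-over differences.

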7.2 INVESTIGATIONAL SITES

Approximately 1-2 sites

7.3 INCLUSION AND EXCLUSION CRITERIA

No deviations to the inclusion or exclusion criteria are permitted.

7.3.1 Inclusion Criteria

All of the following criteria must be met for a subject to participate in the study:

1. Must voluntarily sign and date each Institutional Review Board (IRB)-approved informed consent form (ICF) prior to the initiation of any screening or study-specific procedures.
2. Willing and able to comply with study requirements.
3. Healthy adult subjects 18 to 55 years of age, inclusive at the time of informed consent.
4. Body Mass Index (BMI) of 18-32 kg/m² inclusive
5. Female subjects of childbearing potential must not be planning a pregnancy or be pregnant or lactating. All female subjects must have a negative result for the pregnancy tests performed at screening and each treatment period.

6. Female subjects of childbearing potential (including perimenopausal females who have had a menstrual period within 1 year prior to screening) must agree to use a reliable method of contraception until study completion and for at least 4 weeks following their final study visit. Reliable contraception is defined as a method which results in a low failure rate, i.e., less than 1% per year when used consistently and correctly, such as hormonal contraception (oral, implants, injection, ring, or patch) and intrauterine contraceptive devices (IUDs), at least 3 months prior to Screening, or a vasectomized partner.

Note: complete abstinence from sexual intercourse is an acceptable form of contraceptive practice.

7. Female subjects of non-childbearing potential must be either surgically sterile (hysterectomy, bilateral, tubal ligation, bilateral salpingectomy, and/or bilateral oophorectomy at least 26 weeks before the Screening Visit) or post-menopausal, defined as spontaneous amenorrhea for at least 2 years

Male subjects with partners of childbearing potential must have had surgical sterilization (vasectomy) at least 26 weeks prior to Screening or use a male barrier method of contraception (i.e. male condom with spermicide) during any sexual intercourse from Study Day -1 (beginning of confinement) until 3 months after the Follow-up Visit.

Note: Complete abstinence from sexual intercourse is an acceptable form of contraceptive practice.

8. Male subjects must agree to abstain from sperm donation from initial study drug administration through 3 months after administration of the last dose of study drug.

